Objectives: Determine the feasibility and acceptability of a combined treatment for veterans with comorbid chronic pain and opioid misuse or dependence, as well as assess mechanisms of change during the combined intervention. A secondary objective is to examine weekly progress on specific therapy targets (e.g., pain acceptance, self-compassion, opioid craving) in the interventions in order to identify potential mechanisms of change and to identify the choice of intermediate endpoints for a larger randomized clinical trial. **Approach**—To test the feasibility of recruitment and retention, as well as study weekly progress on treatment targets, within a randomized clinical trial (RCT) of Acceptance and Commitment Therapy (ACT) + Mindfulness-Based Relapse Prevention (MBRP) or treatment as usual for chronic pain and opiate misuse.

Design and Outcomes: Veterans with chronic pain and opiate misuse, abuse, or dependence who are receiving long-term opioid therapy (i.e., 90+ days) will be recruited from the Raymond G Murphy Veterans Affairs (VA) Medical Center in Albuquerque, NM. Treatment will begin in Year 1 and conclude in Year 2 with follow-up assessment lasting through the first quarter of Year 3. At the time of enrolling in the trial, individuals will participate in a baseline assessment including self-report and behavioral measures. Participants ($n = 120$) will then be randomized to one of two treatment conditions: (1) treatment services-as-usual (i.e., standard care) or (2) standard care with eight weeks of group ACT plus four weeks of group MBRP. Participants will complete assessments at baseline (entry into the study), weekly during the first three months of the study (during treatment), three months after entry in the study (end of treatment), and nine months after entry in the study (six months after treatment conclusion).

Self-Report and Behavioral Assessment Batteries—Self-report and behavioral assessments will be used to evaluate study hypotheses. For the follow-up assessments we will use contact information collected at baseline to contact participants by phone one week prior to their scheduled follow-up date.

Participants will be reminded about procedures and scheduled to complete all assessments at the VA.

Demographic Information (Pre-treatment, Post-treatment, and 6 month follow-up assessment): Patient demographics (e.g., gender, age, educational achievement) and pain-related information (e.g., duration, location, history of treatment) will be collected during the pre-treatment assessment. We will re-assess pain-related information and treatment history at post-treatment and the 6-month follow-up assessment.

Clinical Outcome Measures (Pre-treatment, Post-treatment, and 6 month follow-up assessment): Given the relevance of interference from pain on key aspects of functioning in those with chronic pain, we will utilize the NIH PROMIS toolkit measures for pain behavior¹ and pain interference². Both PROMIS measures have evidence of excellent psychometric properties in chronic pain. We will also collect information on current opioid misuse using the Current Opioid Misuse Measure, a measure of aberrant opioid-related behaviors over the past month³. The recommended cut-score of 12 has adequate sensitivity (77%) and specificity (77%) for a current diagnosis of prescription drug abuse³. Finally, current pain intensity, as well as least, most, and average over the past seven days, will be assessed via 0-10 numerical ratings scales and disability will be assessed via the Sickness Impact Profile⁴.

Weekly Self-Report Progress Measures (20 minutes per week): In order to examine our secondary objective concerning mechanisms of change during treatment, we will collect weekly data during the 12 weeks of treatment to assess for change in specific therapy targets that are hypothesized to change during treatment. These weekly progress measures will include three self-report questionnaires, each of which has evidence for mediating treatment outcomes in either ACT for chronic pain⁵ or MBRP for substance use disorder^{6,7}. These measures include:

1. **Chronic Pain Acceptance Questionnaire (CPAQ⁸)**. The CPAQ is a 20-item measure of acceptance and willingness to have chronic pain. It is perhaps the most widely used measure of pain acceptance in

the literature and its psychometric properties, factor structure, and sensitivity to treatment are well established^{9,10}.

2. *Self-Compassion Scale (SCS)*¹¹. The SCS is a 26-item questionnaire which evaluates numerous aspects of mindfulness and self-compassion. Initial psychometric evaluations of the measure have provided support for its reliability and validity¹¹.

3. *Penn Alcohol/Drug Craving Scale (PACS)*¹². A modified version of the PACS will be used to assess both alcohol and drug craving. The PACS is a 5-item measure including questions about frequency, intensity, and duration of craving, and an overall rating of craving for the previous week. The PACS has demonstrated good psychometric properties in our prior studies, including internal consistency reliability ($\alpha=.87$) and criterion validity^{6,7}.

In addition to these three questionnaires, the weekly progress measure will also include items to assess mindfulness practice (days/times per day) and homework assignment completion, as well as items relating to pain intensity, distress intensity, willingness to experience pain, and engagement in valued activity¹³.

Interventions and Duration: Intervention Conditions—All participants will continue to receive standard care for chronic pain within the VA. In addition, one-half of participants will be randomized to also receive ACT plus MBRP. **Standard Care:** Participants in all conditions will receive standard treatment as usual at the VA, as indicated by the individual's treatment plan which will not be manipulated by the research team. Consistent with national and VA standards^{14,15}, care at the recruitment sites typically consists of noninvasive interventions, such as analgesic pain medications (e.g., opioids, NSAIDs, anti-epileptics), topical solutions (e.g., lidocaine), physical therapy, and massage, as well as limited invasive interventions (e.g., injections, radiofrequency denervation). **Acceptance and Commitment Therapy (Weeks 2–9):** The ACT intervention is based on the standardized and manualized protocol of [name] and Sorrell¹⁶, which consists of weekly 90-minute group meetings over eight weeks. The protocol has been successfully used in previous clinical trials (e.g., ^{17,18}) and is currently available on the VA's Evidence-Based Practice SharePoint website. Over the course of the group meetings, participants will identify areas of meaningful functioning that have been adversely impacted by pain, learn methods to enhance pain willingness in the service of these meaningful areas, and practice present-focused awareness skills. Group sessions will include discussions of the impact of pain and distress avoidance, identifying alternatives to this avoidance and establish plans for behavior change, demonstration and role-playing exercises, and homework assignments. Participants will be provided with a treatment manual to help guide and inform practice outside of group sessions. Table 1 provides an outline of session content for the eight week ACT intervention. We anticipate enrolling approximately eight patients per group. **Mindfulness Based Relapse Prevention (Weeks 10–13):** The MBRP program is a standardized group psycho-educational intervention that consists of weekly 90-minute group meetings spanning four¹⁹ to eight weeks²⁰. For the current study, we will use the four-week program, which will eliminate redundancy with the ACT protocol (the eight-week MBRP group has some redundancy with ACT) and will also expand upon the 8 weeks of ACT by focusing on reactivity to substance cues, opioid misuse, and nonjudgmental awareness. Briefly, participants will be instructed in mindfulness techniques aimed at increasing concentration, improving awareness, and cultivating a nonjudgmental and accepting attitude toward craving and automatic thought patterns. Group sessions include discussions of mindfulness as a means of coping with craving and painful cognitions, role-playing exercises, meditation practice, and homework assignments. Each participant will be given audio CDs developed specifically for MBRP for independent practice outside of the group sessions.

Sample Size and Population: This study will recruit veterans with chronic pain ($n = 120$) who are currently misusing, abusing, or dependent on prescription opioids. Participants will be recruited from the Co-Occurring Disorders Clinic (a specialty clinic for patients with chronic pain and evidence of problematic opioid use), as well as the Ambulatory Care and Primary Care Clinics of Raymond G. Murphy VA Medical Center in Albuquerque, New Mexico.

1. STUDY OBJECTIVES

1.1 **Primary Study Aims:** Determine the feasibility of an integrated psychosocial treatment (ACT + MBRP) in veterans with chronic pain with evidence of opioid-related problems. Chronic pain patients ($n = 120$) who are receiving opioid therapy and who are identified as opioid misusing, abusing, or dependent will be recruited from the Albuquerque Veterans Administration (VA) Hospital. Participants will be randomized to receive standard care or standard care in addition to ACT+MBRP. **Hypothesis 1: Feasibility of recruitment:** Given the high prevalence of both chronic pain and opioid-related problems in VA populations, we hypothesize it will be possible to recruit our target sample size ($n = 120$) within a 15-18 month timeframe. **Hypothesis 2: Feasibility of retention:** Drop-out rates will be consistent with other trials of similar psychosocial interventions for chronic pain (i.e., < 20%^{5,21-23}).

1.2 **Secondary Study Aims:** To examine weekly progress on specific therapy targets (e.g., pain acceptance, self-compassion, opioid craving) in the interventions in order to identify potential mechanisms of change and to identify the choice of intermediate endpoints for a larger randomized clinical trial.

Hypothesis 1: Evidence of treatment mechanisms: The combined ACT+MBRP treatments will be associated with changes in treatment mechanisms specified within the therapeutic models and in a manner consistent with that of previous work on ACT and MBRP, in comparison with standard care.

Hypothesis 2: Selection of intermediate endpoints: Weekly progress measures will provide data indicating measures of treatment-specific mechanisms that are most sensitive to change. We hypothesize that acceptance of pain discomfort will be most sensitive to change in ACT and that reductions in reactivity to substance craving will be most sensitive to change in MBRP.

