Analyses to Test Secondary Aim Hypotheses. The primary goal of Aim 2 is to identify potential mechanisms of change and intermediate endpoints for future randomized clinical trials comparing ACT+MBRP to standard care. We will accomplish this goal by examining initial level and changes in targeted mechanisms over time during the course of treatment, as well as the association between changes in targeted mechanisms during treatment and 6-month follow-up measures of clinical outcomes. Targeted mechanisms will include (1) pain acceptance (2) psychological flexibility, (3) experiential avoidance, (4) opioid craving, and (5) reactivity to pain and craving, and will be examined using latent growth curve models with fixed effects of treatment and random effects of time. These analyses will provide an estimate of the initial level of each targeted mechanism (i.e., intercept) and the change in the targeted mechanisms over time (slope). Clinical outcome measures will include pain interference, pain behavior, and opioid misuse and will be examined using mediation analyses within the context of latent growth curve modeling⁶⁴, as we have done in prior studies^{63,65}. Specifically, as shown in simplified form in Figure 2, we will examine whether initial level (intercept) or changes (slope) in the targeted mechanisms ("M" in figure 2) during treatment mediate the effect of treatment on 6-month clinical outcomes, controlling for baseline levels of the outcomes. These analyses will also provide a test of Aim 2 Hypothesis 2, which is to identify those measures that are most sensitive to change (measures with the largest slope). Identifying measures that are more sensitive to change will help us in identifying intermediate endpoints for a larger RCT. Validation of intermediate endpoints is challenging and it is often recommended that meta-analytic methods be used⁶⁶, but alternative methods have been developed that allow for the evaluation of endpoints in mental-health clinical trials⁶⁷.

Figure 2. Simplified mediation model (excludes residual terms and covariances)

models will be estimated using the product of coefficients method⁶⁸, which provides an estimate of the mediated effect by multiplying regression coefficients for the regression of the mediators (e.g., slope of targeted mechanism) on treatment condition (i.e., a-path or α) and for the regression of the clinical

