outcome on the mediators (i.e., b-path or β). We will use bootstrapping to obtain 95% confidence intervals of the mediated effect⁶⁹. We will use maximum likelihood estimation for all analyses, which provides the variance-covariance matrix for all available data and is the preferred method for estimation when some data are missing⁷⁰. Attrition analyses will determine whether there are any differences in study variables between those with missing and complete data. Study variables associated with missing data will be covaried in all analyses.

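### Section 9.1 ranks mechanisms by largest observed slope to help choose intermediate endpoints, but plans no measure of how uncertain that ranking is

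*Combined protocol and SAP*

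**What the plan says.** The synopsis (Objectives) and section 1.2 give Aim 2 a practical purpose: "to identify the choice of intermediate endpoints for a larger randomized clinical trial". Hypothesis 2 in section 1.2 expects that "Weekly progress measures will provide data indicating measures of treatment-specific mechanisms that are most sensitive to change". It names the expected leaders in advance: pain acceptance for ACT and reactivity to craving for MBRP.

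Section 9.1 supplies the criterion. The growth-curve analyses are to "identify those measures that are most sensitive to change (measures with the largest slope"). It then says how the result is used: "Identifying measures that are more sensitive to change will help us in identifying intermediate endpoints for a larger RCT". The same aim also draws on the "association between changes in targeted mechanisms during treatment and 6-month follow-up measures of clinical outcomes", examined by mediation.

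The candidates are not the same throughout. Section 9.1 lists five: "Targeted mechanisms will include (1) pain acceptance (2) psychological flexibility, (3) experiential avoidance, (4) opioid craving, and (5) reactivity to pain and craving". The synopsis says "These weekly progress measures will include three self-report questionnaires", and it adds single diary items.

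On precision, section 9.1 says: "We will use bootstrapping to obtain 95% confidence intervals of the mediated effect". It plans no interval for a slope, a difference between slopes or a rank. It also does not say whether slopes are standardised, or whether slope means change within an arm or the difference between arms.

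**The concern.** The largest of several noisy estimates tends to be too large, and it may belong to a measure that is not truly the most responsive. Ranking by point estimate alone hides both problems. A narrow lead and a wide lead are reported in the same way.

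At stake is the evidence that Aim 2 passes to the larger trial. A measure could be put forward as most sensitive when the data barely separate it from the next, and its observed effect would look better than it is. The hypotheses about which measure leads are comparative claims, yet no comparison between measures is planned with its uncertainty.

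**Working it through.** **The plan's own figure.** Section 9.2 gives 60 per arm for 80% power at d = 0.25, with three assessments, correlation 0.43 and two-sided alpha 0.05. A group-by-time F test reproduces it: f = 0.25/2 = 0.125; lambda = 0.125² × 120 × 3/(1 − 0.43) = 9.87; df 2 and 236; power 0.805. That calculation concerns clinical outcomes. The plan gives no figure for the precision of the slope ranking.

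**Inputs from the documents.** n = 60 per arm and d = 0.25 (section 9.2); K = 5 mechanisms (section 9.1) or K = 3 questionnaires (synopsis); drop-out under 20% (section 1.1), so 48 per arm at that limit.

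**Assumptions.** Treatment effects on slope are in SD units on a common scale. The correlation r between the estimates for different measures is 0.3 to 0.7. The d of 0.25 is carried over from clinical outcomes to mechanisms.

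**Standard error.** SE = sqrt(2/60) = 0.183. As a check, a weekly growth model with 12 or 13 points gives 0.123 to 0.222 for slope variances assumed between 0 and 1, so 0.183 lies inside that range.

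**Equal true effects.** Expected winner = d + c × SE × sqrt(1 − r), with c = 1.163 for five measures and 0.846 for three.
- Five, r = 0.3: 0.25 + 1.163 × 0.183 × 0.837 = 0.428, which is 71% too high.
- Five, r = 0.7: 0.25 + 1.163 × 0.183 × 0.548 = 0.366, which is 47% too high.
- Three, r = 0.3: 0.25 + 0.846 × 0.183 × 0.837 = 0.379, which is 52% too high.
- Three, r = 0.7: 0.25 + 0.846 × 0.183 × 0.548 = 0.335, which is 34% too high.

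**Other patterns.** These come from simulation (400,000 draws per case). Overstatement is the mean winning estimate divided by the mean true effect of the measure selected, minus 1. Entries are for r = 0.3 / 0.5 / 0.7.

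| True effects | Overstatement, K = 5 (%) | Overstatement, K = 3 (%) | Best ranks first, K = 5 (%) | Best ranks first, K = 3 (%) |
|---|---|---|---|---|
| All 0.25 | 71 / 60 / 47 | 52 / 44 / 34 | no best | no best |
| All 0.50 | 36 / 30 / 23 | 26 / 22 / 17 | no best | no best |
| One 0.40, rest 0.25 | 48 / 37 / 23 | 31 / 24 / 15 | 49 / 55 / 65 | 63 / 68 / 77 |
| One 0.50, rest 0.25 | 27 / 18 / 8 | 17 / 11 / 4 | 69 / 77 / 88 | 80 / 86 / 93 |

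**Sensitivity.**
- At 48 per arm with all effects 0.25, overstatement is 52-80% (five) or 38-58% (three).
- At 48 per arm, a measure at 0.40 among five ranks first in 45-60% of trials.
- If slope means within-arm change of 0.5 SD, overstatement with five measures at r = 0.5 is about 14-26%, using the growth-model standard errors.

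**The case against.** The strongest reply is that the plan does not let the ranking decide alone. A reader might infer that the endpoint simply is the measure with the largest slope. Section 9.1 says only that sensitivity helps in the choice. It sets the ranking beside mediation with bootstrap intervals and acknowledges that validating intermediate endpoints is difficult, and section 1.2 names expected leaders beforehand. This stands, and it limits the point to how the ranking is reported. It does not remove the point: Hypothesis 2 is tied to the largest slope, and no rule says how slope rank and mediation are to be combined.

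A reader might also infer that an inflated slope will set the size of the larger trial. No passage says so, and an intermediate endpoint need not be the one a trial is sized on. No sample-size or power consequence can be attributed to this plan.

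Third, d = 0.25 is the plan's minimum average effect, stated for clinical outcomes. Section 9.2 cites ACT effects from 0.29 to 1.09 and MBRP effects from 0.21 to 0.52. A general claim that the winner is overstated by half or more therefore fails. It needs near-equal effects around 0.25 and, for the most part, five candidates.

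Fourth, when effects are close, choosing the wrong measure costs little, and when one clearly leads it is usually found. That is fair as to the choice. But overstatement is greatest when effects are close, so the reported effect misleads most there.

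Finally, this is a secondary aim of a feasibility trial, and carrying the leading measure forward on its point estimate is defensible. That bears on the remedy: it argues for showing the uncertainty, not for forbidding a choice.

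**Conclusion.** The point holds as a gap in reporting. Section 9.1 ranks mechanisms by observed slope for a stated purpose and plans nothing to show how uncertain the ranking is.

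The size depends on assumptions the documents do not settle: the correlation between measures, the spread of true effects, the number of candidates, and d = 0.25 applied to mechanisms. With equal effects of 0.25, the overstatement at 60 per arm is material for either count of candidates. It shrinks as effects grow or separate, to about 4% at the most favourable case examined. With a moderate true leader (0.40 against 0.25), the ranking misses it in roughly a quarter to a half of trials.

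The documents do not support saying that endpoints are chosen on slope alone, that the slope will size the next trial, or that overstatement of half or more is to be expected in general.

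**What to change.** In section 9.1:

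- For each mechanism, report the standardised treatment effect on slope with a 95% confidence interval.
- Resample participants jointly across all measures. Report intervals for the pairwise differences and the proportion of resamples in which each measure ranks first.
- Describe near-ties as ties, and weigh the ranking together with the mediation results.
- If the leading effect is used for planning, use a selection-corrected estimate, such as a bootstrap bias-corrected or shrunken one.

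Do not require the lead over the runner-up to exclude zero before naming a leader. With one measure at 0.40 and the rest at 0.25, and r = 0.3 to 0.5, that rule would name one in only about 1-5% of trials.

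The cost is some wording and a modest extension of the bootstrap already planned, with no new data or visits. The downside is that the ranking may have to be reported as uncertain.

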2. BACKGROUND AND RATIONALE

2.1 Background on Condition, Disease, or Other Primary Study Focus

Prescription drug abuse and opioid use disorders are a significant public health problem in the United States. According to the most recent data from the National Survey on Drug Use and Health²⁴, approximately 13% of the U.S. population (more than 34 million people) aged 12 or older reported lifetime nonmedical use of prescription pain relievers. Likewise, in 2011, nearly two million Americans reported abuse or dependence on prescription pain relievers within the past year. Since 1999, there has been a 300% increase in overdose deaths caused by prescription opioids, with 14,800 overdose deaths in 2008 alone.²⁵ Overdose deaths due to opioids are more common than overdose deaths due to cocaine and heroin combined²⁶. The societal costs of prescription opioid misuse, abuse, and dependence was estimated at \$55.7 billion in 2007, with workplace and healthcare costs accounting for 91% and criminal justice approximately 9% of those costs²⁷.

Substantial increases in morbidity and mortality associated with opioid misuse are particularly relevant in the case of chronic pain, a common healthcare concern in primary and specialist care settings^{28,29} costing approximately \$100 billion annually in the United States^{30,31}. The available evidence suggests opioids are increasingly used in the treatment of chronic pain³² with a recently published study indicating that 61% of 26,000 primary care patients surveyed were on long-term (i.e., 90+ consecutive days) chronic opioid therapy³³. Unfortunately, aberrant opioid use behaviors, such as opioid dependence and overuse or use of other substances, are quite common, occurring in up to 25% of patients on long-term opioid therapy^{34,35}. Furthermore, while comprehensive psychosocial treatments that address pain-related distress and disability have a strong evidence base³⁶, patients meeting criteria for opioid dependence are at risk for poorer outcomes and noncompletion³⁷. Therefore, development of interventions that address the core issues of distress and disability as well as aberrant opioid use are a high priority.

In military veterans, the issues of chronic pain and opioid-related problems seem even more pronounced. Chronic pain is common, distressing, and debilitating, particularly in those that have served since the first Gulf War, with prevalence estimates reaching as high as 68%³⁸⁻⁴². As in civilian healthcare settings, opioids are commonly - and increasingly - used in the treatment of chronic pain in veterans^{38,43}, with one recent large scale study indicating that two-thirds (978 of 1,478) of veterans with a chronic pain diagnosis were prescribed opioids as part of their treatment⁴⁴. Furthermore, in that same study, half of those prescribed opioids (478 of 978) were receiving in excess of 180 mg total daily morphine milligram equivalents, a level that represents a substantial increase in overdose risk in comparison with lower dosages⁴⁵. There is evidence of a vicious cycle of comorbidity amongst chronic pain, opioid abuse, and adverse events in veterans^{46,47}. For example, in one study of over 6,000 veterans, the mere presence of a chronic pain diagnosis almost doubled the risk of prescription drug abuse (OR: 1.9; 95% CI: 1.4-2.5)⁴⁸, while another large scale survey of over 15,000 veterans indicated a prescription for opioids for chronic pain was related with an increased risk of adverse clinical outcome (e.g., accidents resulting in wounds, opioid-related accidents, overdose, violence-related injuries) in a manner that was independent of mental health diagnoses or other prescribed medications⁴³. Clinicians in Veteran Affairs (VA) hospitals are well aware of these issues and have noted both frustration and uncertainty in treating chronic pain patients, as well as the lack of evidence-based approaches that simultaneously treat problems related to both chronic pain and opioid misuse^{49,50}.

